## **5.2 SAMPLE STORAGE, TRACKING AND DISPOSITION**

Samples will be ordered in CRIS and tracked through a Clinical Trial Data Management system. Should a CRIS screen not be available, the CRIS downtime procedures will be followed. Samples will not be sent outside NIH without IRB notification and an executed MTA.

Paraffin embedded tissue blocks and unstained slides will be stored at NCI Laboratory of Pathology located at Building 10.

All specimens obtained in the protocol are used as defined in the protocol. Any specimens that are remaining at the completion of the protocol will be stored in the conditions described above. The study will remain open so long as sample or data analysis continues. Samples from consenting subjects will be stored until they are no longer of scientific value or if a subject withdraws consent for their continued use, at which time they will be destroyed. The PI will report any loss or destruction of samples to the NCI IRB as soon as he is made aware of such loss.

If the patient withdraws consent the participant's data will be excluded from future distributions, but data that have already been distributed for approved research use will not be able to be retrieved.

The PI will report destroyed samples to the IRB if samples become unsalvageable because of environmental factors (ex. broken freezer or lack of dry ice in a shipping container) or if a patient withdraws consent. Samples will also be reported as lost if they are lost in transit between facilities or misplaced by a researcher. Freezer problems, lost samples or other problems associated with samples will also be reported to the IRB, the NCI Clinical Director, and the office of the CCR, NCI.

## **6 DATA COLLECTION AND EVALUATION**

### **6.1 DATA COLLECTION**

The PI will be responsible for overseeing entry of data into an in-house password protected electronic system and ensuring data accuracy, consistency and timeliness. Data will be entered into the C3D Database. The MDASI-BT responses will be entered by study subjects directly into Labmatrix via Scribe. Actigraph data will be downloaded from the device using ActiLife Software. The principal investigator, associate investigators/research nurses and/or a contracted data manager will assist with the data management efforts. All data obtained during the conduct of the protocol will be kept in secure network drives or in approved alternative sites that comply

*Abbreviated Title: Ph II Sunitinib CNS Sarcomas*

*Version Date: 05-30-18*

with NIH security standards. Primary and final analyzed data will have identifiers so that research data can be attributed to an individual human subject participant.

All adverse events, including clinically significant abnormal findings on laboratory evaluations, regardless of severity, will be followed until return to baseline or stabilization of event. Patients will be followed for adverse events for 30 days after removal from study treatment or until off-study, whichever comes first.

An abnormal laboratory value will be considered an AE if the laboratory abnormality is characterized by any of the following:

- Results in discontinuation from the study
- Is associated with clinical signs or symptoms
- Requires treatment or any other therapeutic intervention
- Is associated with death or another serious adverse event, including hospitalization.
- Is judged by the Investigator to be of significant clinical impact
- If any abnormal laboratory result is considered clinically significant, the investigator will provide details about the action taken with respect to the test drug and about the patient's outcome.

**End of study procedures:** Data will be stored according to HHS, FDA regulations, and NIH Intramural Records Retention Schedule as applicable.

**Loss or destruction of data:** Should we become aware that a major breach in our plan to protect subject confidentiality and trial data has occurred, the IRB will be notified.

## 6.2 DATA SHARING PLANS

### 6.2.1 Human Data Sharing Plan

#### What data will be shared?

I will share human data generated in this research for future research as follows:

De-identified data in an NIH-funded or approved public repository.

De-identified data in BTRIS (automatic for activities in the Clinical Center)

De-identified or identified data with approved outside collaborators under appropriate agreements.

#### How and where will the data be shared?

Data will be shared through:

An NIH-funded or approved public repository. Insert name or names: [Clinicaltrials.gov](https://clinicaltrials.gov)

BTRIS (automatic for activities in the Clinical Center)

Approved outside collaborators under appropriate individual agreements.

Publication and/or public presentations.

*Abbreviated Title: Ph II Sunitinib CNS Sarcomas*

*Version Date: 05-30-18*

## When will the data be shared?

Before publication.  
 At the time of publication or shortly thereafter.

## 6.3 RESPONSE CRITERIA

### 6.3.1 Definitions

Evaluable for toxicity: All patients will be evaluable for toxicity from the time of their first treatment with sunitinib.

Evaluable for objective response: Only those patients who have measurable disease present at baseline, have received at least one cycle of therapy, and have had their disease re-evaluated will be considered evaluable for response. These patients will have their response classified according to the definitions stated below. (Note: Patients who exhibit objective disease progression prior to the end of cycle 1 will also be considered evaluable.)

Evaluable Non-Target Disease Response: Patients who have lesions present at baseline that are evaluable but do not meet the definitions of measurable disease, have received at least one cycle of therapy, and have had their disease re-evaluated will be considered evaluable for non-target disease. The response assessment is based on the presence, absence, or unequivocal progression of the lesions.

### 6.3.2 Disease Parameters

Measurable disease: Based on RANO criteria [16]

### 6.3.3 RANO Criteria for Response

RANO Criteria for Response (34)	CR	PR	SD	PD
T1 gadolinium enhancing disease	None	$\geq 50\% \downarrow$	$< 50\% \downarrow$ but $< 25\% \uparrow$	$\geq 25\% \uparrow^1$
T2/FLAIR	Stable or $\downarrow$	Stable or $\downarrow$	Stable or $\downarrow$	$\uparrow^1$
New lesion	None	None	None	Present 
Corticosteroids	None	Stable or $\downarrow$	Stable or $\downarrow$	n/a †
Clinical status	Stable or $\uparrow$	Stable or $\uparrow$	Stable or $\uparrow$	$\downarrow^1$
Requirement for response	All	All	All	Any 

 Progression occurs when this criterion is present

†Increase in corticosteroids alone will not be taken into account in determining progression in the absence of persistent clinical deterioration.

$\downarrow$  = decreased,  $\uparrow$  = increased,

CR = complete response, PR = partial response, SD = stable disease, PD = progressive disease. If PD is unclear based on white matter changes, patients may be kept on trial.

FLAIR, fluid-attenuated inversion recovery; NA, not applicable.

### 6.3.3 Evaluation of Best Overall Response

- 6.3.3.1 Duration of overall response: The duration of overall response is measured from the time measurement criteria are met for CR or PR (whichever is first recorded) until the first date that recurrent or progressive disease is objectively documented (taking as reference for progressive disease the smallest measurements recorded since the treatment started).
- 6.3.3.2 The duration of overall CR: duration of overall CR is measured from the time measurement criteria are first met for CR until the first date that progressive disease is objectively documented.
- 6.3.3.3 Duration of stable disease: Stable disease is measured from the start of the treatment until the criteria for progression are met, taking as reference the smallest measurements recorded since the treatment started, including the baseline measurements.

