## 1. INTRODUCTION

### 1.1 STUDY OBJECTIVES

#### 1.1.1 Primary Objective:

To determine the anti-tumor effect of sunitinib in recurrent gliosarcomas and primary CNS sarcomas as assessed by objective response rate (ORR).

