### 6.3.5 Response Review

All subjects will be evaluated by cranial imaging every 6 weeks.

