## 8 STATISTICAL CONSIDERATIONS

### 8.1 GENERAL APPROACH

We monitor the ORR using the Bayesian optimal phase 2 (BOP2) design [18]. Specifically, let  $n$  denote the interim sample size and  $N$  denote the maximum sample size. Let  $p$  denote the ORR and define the null hypothesis  $H_0: p \leq 0.2$ , representing that the treatment is ineffectual. We will stop enrolling patients and claim that the treatment is not promising if

$$Pr(p > 0.2 | data) < \lambda \left(\frac{n}{N}\right)^\alpha,$$

where  $\lambda=0.85$  and  $\alpha=0.8$  are design parameters optimized to minimize the chance of incorrectly claiming that an efficacious treatment is not promising (i.e., type II error) under the alternative hypothesis  $H_1: p = 0.4$ , while controlling the type I error rate at 0.1 (i.e., the chance of incorrectly claiming that an ineffectual treatment is promising is no more than 10%).

Assuming a Beta(0.2,0.8) prior distribution for  $p$ , the above decision rule corresponds to the following stopping boundaries and yields a statistical power of 0.8537 under  $H_1$ :

**Table 1.** Stopping boundaries

# patients treated	Stop if # responses <=
16	3
24	5
32	9

Based on Table 1, we perform the interim and final analysis when the number of enrolled patients reaches 16, 24 and 32. If the number of responses fails to exceed the stopping boundary, we will suspend accrual, inspect the efficacy data and make the go/no-go decision based on both the ORR and other clinical considerations (e.g., PFS).

*Abbreviated Title: Ph II Sunitinib CNS Sarcomas*

*Version Date: 05-30-18*

Below are the operating characteristics of the design based on 10000 simulations using the BOP2 web application, which is available at <http://www.trialdesign.org>.

ORR	Early stopping (%)	Claim promising (%)	Sample size
0.1	97.95	0.05	16.7
0.2	71.74	8.00	21.5
0.3	31.45	46.22	27.5
0.4	7.92	85.37	30.8
0.5	1.31	98.13	31.8

We monitor the rate of Dose Limiting Toxicity (DLT) independently for each cohort using the following Bayesian rule: stop enrolling patients to a cohort if  $\text{Pr}(\text{DLT} > 30\% \mid \text{data}) > 0.9$ . That is, we will stop enrolling patients to a cohort if the data indicate that there is more than 90% chance that the true DLT rate is higher than 30%. This posterior probability is calculated based on the beta-binomial model. The decision rule gives the following stopping rule, assuming a Beta(0.1, 0.4) prior distribution for DLT rate,

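### CR and PR need no confirmation, so as written one qualifying scan counts toward the primary ORR and the Table 1 boundaries

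*Combined protocol and SAP*

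**What the plan says.** The primary objective (section 1.1.1) is anti-tumor effect "as assessed by objective response rate (ORR"). Section 8.1 compares the response count with stopping boundaries of 3, 5 and 9 at 16, 24 and 32 patients.

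Four places bear on who counts as a responder:

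- **Section 6.3.1** makes a patient evaluable for response after measurable baseline disease, one cycle of treatment and a re-evaluation. Response is then classified by the definitions that follow. No second scan is asked for.
- **Section 6.3.3, the table headed "RANO Criteria for Response (34")**, sets conditions for PR on enhancing disease (a fall of at least 50%), T2/FLAIR, new lesions, corticosteroids and clinical status. All must be met. No row covers confirmation or minimum duration.
- **Section 6.3.3, Evaluation of Best Overall Response** (the same number is used twice), defines durations only. Duration of response is "measured from the time measurement criteria are met for CR or PR (whichever is first recorded"). No rule for deriving best overall response is given.
- **Section 8.3** describes how ORR is summarised and adds no confirmation rule.

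Section 6.3.5 sets the scan schedule: "All subjects will be evaluated by cranial imaging every 6 weeks".

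**The concern.** A best response taken over repeated scans needs only one favourable reading. Sunitinib inhibits VEGFR1 to 3 (section 1.2.3), and contrast enhancement can fall under such a drug without lasting tumor shrinkage. Ordinary measurement error can also carry a tumor across the 50% line once. The T2/FLAIR, new-lesion, steroid and clinical conditions screen out some of these readings, but they are judged at the same assessment and do not test whether the response lasts.

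The stake is the go/no-go decision. Section 8.1 undertakes that "the chance of incorrectly claiming that an ineffectual treatment is promising is no more than 10" per cent. That undertaking concerns whatever rate the 20% null describes. If the null means confirmed or durable responses while the count includes unconfirmed ones, the two sides of the comparison differ.

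**Working it through.** **1. Reproduce the design.** Inputs from section 8.1: null 0.20, alternative 0.40, λ = 0.85, α = 0.8, prior Beta(0.2, 0.8), looks at n = 16, 24, 32. The rule stops if Pr(p > 0.2 | data) < 0.85 × (n/32)^0.8.

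| n | Cut-off | Posterior probability at the boundary | One response more |
|---|---|---|---|
| 16 | 0.488 | 0.401 (3 responses) | 0.644 |
| 24 | 0.675 | 0.501 (5 responses) | 0.691 |
| 32 | 0.850 | 0.846 (9 responses) | 0.922 |

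The boundaries 3, 5, 9 are as in Table 1. An exact binomial recursion over the three looks gives a probability of claiming promise of 8.07% at ORR 0.20 (stated 8.00%), 47.0% at 0.30 (stated 46.22%) and 85.55% at 0.40. The plan says the rule "yields a statistical power of 0.8537 under" the alternative. The design reproduces within simulation error.

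**2. How much spurious response the error cap can absorb.** Suppose 0.20 is the confirmed rate and a share f of the other patients is counted on one scan. Then counted ORR = 0.20 + 0.80f. The documents give no value for f; it is an assumption.

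| f (assumed) | Counted ORR | False-claim probability |
|---|---|---|
| 0 | 0.200 | 8.1% |
| 2% | 0.216 | 12.1% |
| 2.5% | 0.220 | 13.3% |
| 5% | 0.240 | 20.1% |
| 10% | 0.280 | 37.4% |

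The 10% cap is reached at a counted ORR of about 0.208, that is f = 0.008/0.80 = 1%. On 32 patients this is 0.008 × 32 ≈ 0.26 of a patient.

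**3. What confirmation does for one tumor.** Assumptions, none from the documents: error SD of the bidimensional product 0.10 to 0.20 on the log scale, a baseline error shared by three on-treatment scans, and PR read when log(scan/baseline) ≤ log 0.5. Simulated probabilities:

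| True reduction | PR on any of 3 scans | PR on 2 consecutive scans |
|---|---|---|
| 0% | 0.00–0.02 | below 0.01 |
| 30% | 0.02–0.25 | 0.00–0.06 |
| 40% | 0.22–0.48 | 0.05–0.18 |
| 55% | 0.87–0.94 | 0.58–0.73 |
| 65% | 0.98–1.00 | 0.88–0.99 |

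Confirmation removes most false readings near the cut-off, but it also loses a sizeable share of genuine responses just beyond it. The model covers lesion size only and gives every patient three scans, although treatment stops at progression. Transient shrinkage is not modelled.

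**4. The price in power.** If 0.40 was an unconfirmed rate and a share L of responses is not confirmed, the tested rate is 0.40 × (1 − L). With L = 10% it is 0.36 and power is 73.3%; with L = 20% it is 0.32 and power is 56.5%; with L = 0 it is 85.5%.

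**The case against.** Four points can fairly be made against this.

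- **The sentence in 6.3.3.1 does not define a responder.** A reader might infer that it does. It only starts the clock for duration, and the fix keeps it. The gap lies in 6.3.1 and the response table, and it is an absence of a rule rather than a stated single-scan rule.
- **The criteria carry the RANO name, and section 6.3.2 cites reference 16.** A persistence rule may have been meant by reference. But 6.3.2 cites that source for measurable disease, the protocol prints its own response table, and the table's "(34)", if a citation, has no entry in a reference list that ends at 16. Nothing says that an outside rule applies. An intended rule would still need to be written down.
- **The false-claim rate may not be inflated at all.** Section 8.1 calls p only the ORR. If 20% and 40% are both unconfirmed rates, counting unconfirmed responses is consistent and the 8% stands. Section 1.2.4 (Past Experience) was not in the text available here and may settle this. The objection stands and makes the size conditional.
- **Safeguards exist.** PR needs every condition in the table, section 4 delays imaging after a recent steroid increase, and duration of response and PFS would expose short-lived responses. These help, but none tests persistence before a response enters the Table 1 count. Section 8.1 lets other considerations such as PFS inform the decision only after a boundary has not been exceeded.

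**Conclusion.** The gap is real: nothing in the available text requires a CR or PR to persist, and read as written a single qualifying scan counts toward the primary ORR and Table 1. In a trial of a VEGFR inhibitor judged on enhancement, confirmation at a scan already on the schedule is a better rule and a cheap one to run.

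The size rests on two things that the documents do not give: that 20% is a confirmed or durable rate, and how often spurious responses occur. On the first assumption the 10% cap has room for less than one percentage point of extra response, and the false-claim probability would be 13.3% at a counted ORR of 22% and 20.1% at 24%.

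A reader might infer that the trial's type I error actually is 13% or 20%. The documents do not support that. Nor do the single-tumor probabilities in step 3 lead to an ORR of 22% or 24%: that would need a distribution of true shrinkage across patients, and none is given.

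**What to change.** In sections 6.3.3 and 8.1:

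1. Count a patient as a responder for Table 1 and the final ORR only if CR or PR criteria are still met at the next scheduled 6-week scan, at least 4 weeks after the first qualifying one.
2. Keep dating duration of response from the first qualifying scan.
3. Report unconfirmed responses separately, and count patients who leave before the confirmatory scan as unconfirmed, keeping them in the denominator.
4. State that the 20% and 40% rates are on the confirmed basis. If 40% was an unconfirmed rate, restate the power.
5. Section 8.1 triggers looks by number enrolled. Hold each look until responses pending at that point are resolved.

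Cost: wording only, with no extra scans, because imaging every 6 weeks is already planned. The downsides are a lower ORR, including some genuine responses close to the 50% line; a wait of about 6 weeks at looks with pending responses; and possibly the loss of power shown in step 4.

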### 6.3.4 Progression-Free Survival

PFS is defined as the duration of time from start of treatment to time of progression or death, whichever occurs first. In cases where this might be unclear, patients may continue on trial.

### 6.3.5 Response Review

All subjects will be evaluated by cranial imaging every 6 weeks.

## 6.4 TOXICITY CRITERIA

The following adverse event management guidelines are intended to ensure the safety of each patient while on the study. The descriptions and grading scales found in the revised NCI Common Terminology Criteria for Adverse Events (CTCAE) version 5.0 will be utilized for AE reporting. All appropriate treatment areas should have access to a copy of the CTCAE version 5.0. A copy of the CTCAE version 5.0 can be downloaded from the CTEP web site ([http://ctep.cancer.gov/protocolDevelopment/electronic\\_applications/ctc.htm](http://ctep.cancer.gov/protocolDevelopment/electronic_applications/ctc.htm)).

## 7 SAFETY REPORTING REQUIREMENTS/DATA AND SAFETY MONITORING PLAN

### 7.1 DEFINITIONS

#### 7.1.1 Adverse Event

Any untoward medical occurrence in a human subject, including any abnormal sign (for example, abnormal physical exam or laboratory finding), symptom, or disease, temporally associated with the subject's participation in research, whether or not considered related to the subject's participation in the research.

#### 7.1.2 Suspected adverse reaction

Suspected adverse reaction means any adverse event for which there is a reasonable possibility that the drug caused the adverse event. For the purposes of IND safety reporting, 'reasonable possibility' means there is evidence to suggest a causal relationship between the drug and the

*Abbreviated Title: Ph II Sunitinib CNS Sarcomas*

*Version Date: 05-30-18*

adverse event. A suspected adverse reaction implies a lesser degree of certainty about causality than adverse reaction, which means any adverse event caused by a drug.

#### 7.1.3 Unexpected adverse reaction

An adverse event or suspected adverse reaction is considered “unexpected” if it is not listed in the investigator brochure or is not listed at the specificity or severity that has been observed; or, if an investigator brochure is not required or available, is not consistent with the risk information described in the general investigational plan or elsewhere in the current application. “Unexpected” also refers to adverse events or suspected adverse reactions that are mentioned in the investigator brochure as occurring with a class of drugs or as anticipated from the pharmacological properties of the drug, but are not specifically mentioned as occurring with the particular drug under investigation.

#### 7.1.4 Serious

An Unanticipated Problem or Protocol Deviation is serious if it meets the definition of a Serious Adverse Event or if it compromises the safety, welfare or rights of subjects or others.

#### 7.1.5 Serious Adverse Event

An adverse event or suspected adverse reaction is considered serious if in the view of the investigator or the sponsor, it results in any of the following:

- Death,
- A life-threatening adverse drug experience
- Inpatient hospitalization or prolongation of existing hospitalization
- Persistent or significant incapacity or substantial disruption of the ability to conduct normal life functions
- A congenital anomaly/birth defect.
- Important medical events that may not result in death, be life-threatening, or require hospitalization may be considered a serious adverse drug experience when, based upon appropriate medical judgment, they may jeopardize the patient or subject and may require medical or surgical intervention to prevent one of the outcomes listed in this definition.

#### 7.1.6 Disability

A substantial disruption of a person’s ability to conduct normal life functions.

#### 7.1.7 Life-threatening adverse drug experience

Any adverse event or suspected adverse reaction that places the patient or subject, in the view of the investigator or sponsor, at immediate risk of death from the reaction as it occurred, i.e., it does not include a reaction that had it occurred in a more severe form, might have caused death.

#### 7.1.8 Protocol Deviation (NIH Definition)

Any change, divergence, or departure from the IRB-approved research protocol.

*Abbreviated Title: Ph II Sunitinib CNS Sarcomas*

*Version Date: 05-30-18*

#### 7.1.9 Non-compliance (NIH Definition)

The failure to comply with applicable NIH Human Research Protections Program (HRPP) policies, IRB requirements, or regulatory requirements for the protection of human research subjects.

#### 7.1.10 Unanticipated Problem

Any incident, experience, or outcome that:

- Is unexpected in terms of nature, severity, or frequency in relation to
  - (a) the research risks that are described in the IRB-approved research protocol and informed consent document; Investigator's Brochure or other study documents, and
  - (b) the characteristics of the subject population being studied; **AND**
- Is related or possibly related to participation in the research; **AND**
- Suggests that the research places subjects or others at a *greater risk of harm* (including physical, psychological, economic, or social harm) than was previously known or recognized.

